6.8. Final Study Visit or Withdrawal Visit

If the participant decides they no longer wish to participate in study follow-up, that visit will constitute the final study visit. Otherwise, the final study visit will occur at the completion of long-term follow-up, as noted above.

- Record AEs as reported by participant or observed by investigator (RR for NKTR-214, SOC for anti-PD-1 and RT)
- Collect HRQoL questionnaire (RR)
- Perform physical examination (SOC)

7. STUDY PROCEDURES/EVALUATIONS

7.1. Study Procedures/Evaluations

7.1.1. *Demographics (SOC)*

Birth date, gender, race, and ethnicity will be collected at screening (recorded for the study from medical records maintained as part of standard clinical care).

7.1.2. *Medical History (SOC)*

A thorough review of the subject's medical history, taking into account all recent and pertinent medical conditions including prior cancer treatment, will be performed at screening. This will be recorded for the study from medical records maintained as part of standard clinical care.

7.1.3. *Physical Exam (SOC)*

A physical exam will be completed at the time of screening, C1D1, and D1 of each subsequent cycle, safety follow-up, withdrawal visit, and final visit. This will be recorded for the study from medical records maintained as part of standard clinical care

7.1.4. *Vital Signs (SOC)*

Vital signs (blood pressure, pulse, respiratory rate, and temperature) will be recorded at screening, C1D1, and D1 of each subsequent cycle, and safety follow-up. This will be recorded for the study from medical records maintained as part of standard clinical care.

7.1.5. *Adverse events (RR/SOC) and concomitant medications (SOC)*

AEs will be recorded at screening and each clinic and research visit, and at the safety follow-up. All of these recordings will be performed as part of the standard of care. AEs will be assessed as described in Section 9. Concomitant medications will also be assessed at this time point.

7.1.6. *Weight (SOC)*

Weight will be recorded at screening, C1D1, and D1 of each subsequent cycle. This will be recorded for the study from medical records maintained as part of standard clinical care.

7.1.7. *Diagnostic biopsy (SOC)*

An SOC biopsy is required to prove metastatic or recurrent disease. When available in excess of what is required for Surgical Pathology diagnosis, archival FFPE tissue (up to 20 slides of 5um tissue) will be provided to the biological correlates study team.

7.1.8. *Index tumor biopsy (RR)*

A research-related biopsy will be performed by core needle, punch, or incisional technique at the discretion of the surgeon/interventional radiologist on day 8 (+/- 5 days) of cycle 2.

7.1.9. *Blood draw (RR)*

Blood will be collected (10 mL each in separate tubes for PBMC and serum) and sent on ice immediately to the UW H&N SPORE Pathology Core facility or the [name] lab for processing and storage prior to treatment infusion on Day 1 of C1, C2, and C3, at Day 8 of C1, C2, and C3, and at the safety follow-up.

7.1.10. ECOG Performance Status (SOC)

Determination of the subject's performance scale based on the ECOG rating scale (Appendix D) will be made at the time of screening, C1D1, D1 of each subsequent cycle, and safety follow-up. This will be recorded for the study from medical records maintained as part of standard clinical care. KPS scores will be converted to ECOG ratings using a conversion table (Appendix E).

7.1.11. Quality of Life Measures (RR)

Quality of life (HRQoL) surveys will be collected at screening/baseline, C1D8, C2C8, C3+D1 (every 4 cycles), at safety follow-up, and at long-term follow-up or withdrawal. The surveys are anticipated to take ~ 10 minutes to complete.

- EORTC QLQ-C30
- EORTC QLQ-H&N35
- EQ-5D

The completion of HRQoL surveys is a research procedure.

Validated health outcome surveys will be used to assess subject perception of mental and physical health, HRQoL, and cancer-related H&N functioning (11).

Each subject will serve as his or her own control with complete HRQoL evaluation prior to and following treatment. Current phase III NRG trials evaluating quality of life have not defined a minimally important difference using the above selected quality of life metrics, and further work is needed for this to be robustly defined. However, the EORTC QLC-C30 has been shown to be robust across trials and will allow for comparison of QOL to prior studies. This will take into account various baseline dysfunctions that may be present due to metastatic head and neck cancer.

Perception of general health and HRQoL will be evaluated using the European Organization for Research and Treatment of Cancer Core Quality of Life Questionnaire (EORTC QLQ-C30) and EQ-5D (12) (13, 14). The EORTC QLQ-C30 was chosen for its sensitivity to cancer-related quality of life and symptomatology, such as nausea/vomiting, fatigue and pain, and because it was identified previously as being well-developed, reliable, valid, and responsive (15). The EQ-5D was chosen due to its wide use in assessing generic health status. It assesses five dimensions of health status: mobility, self-care, usual abilities, pain/discomfort, and anxiety/depression (16).

Specific cancer-related H&N functioning will be assessed with the EORTC QOL Questionnaire H&N35 (EORTC QLQ-H&N35) (17, 18). This validated instrument incorporates items related to swallowing, eating, dry mouth, and saliva production and is sensitive to cancer site and stage (17). The EORTC QLQ-C30 and QLQ-H&N35 will be administered together and will yield a global health status score.

7.1.12. Diagnostic Imaging (SOC)

Diagnostic imaging will be performed at screening, prior to cycle 3, and then every four cycles. Imaging studies can be obtained at any time if clinically indicated by the treating physician.

Imaging studies shall consist of a CT neck to evaluate locoregional disease status and a PET/CT or CT of the chest, abdomen, and pelvis to evaluate known systemic disease status.

Imaging studies are standard clinical care procedures being done within routine care guidelines.

7.2. Laboratory Procedures/Evaluations

Laboratory testing will be completed by CLIA-certified labs.

7.2.1. Clinical Laboratory Evaluations

Complete Blood Count with Differential (SOC)

Blood will be drawn for CBC with differential at screening, and prior to treatment infusion on C1D1, D1 of each subsequent cycle, and at safety follow-up. This is part of the standard of care for anti-PD-1 therapy.

The CBC will include red blood cell count, hemoglobin, hematocrit, WBC count with differential including % neutrophils, lymphocytes, monocytes, eosinophils and basophils, absolute neutrophil count, and platelet count.

Serum Chemistries (SOC)

Blood will be drawn for serum chemistries at screening, C1D1, D1 of each subsequent cycle, and at safety follow-up. This is part of the standard of care for anti-PD-1 therapy.

The serum chemistries will include sodium, potassium, chloride, bicarbonate, blood urea nitrogen (BUN), creatinine, glucose, aspartate aminotransferase (AST), alanine aminotransferase (ALT), alkaline phosphatase, total bilirubin, calcium, protein, albumin, phosphorus, amylase, and lipase.

Pregnancy Test (SOC)

A urine pregnancy test will be completed within 7 days of registration and within 7 days C1D1. Women who are postmenopausal for at least 1 year or surgically sterile (bilateral tubal ligation, bilateral oophorectomy, or hysterectomy) are not considered to be of childbearing potential.

Pregnancy testing is being done as part of standard clinical care.

Thyroid Function Tests (SOC)

Blood will be drawn for serum analysis of TSH and free T4 at screening, prior to even cycles, and at safety follow-up. This is a standard clinical procedure performed within routine guidelines for participants receiving anti- PD-1 therapy.

Electrocardiogram (EKG) (RR)

A standard 12-lead EKG will be obtained at screening to evaluate for QT prolongation.

7.2.2. Specimen Preparation, Handling, and Storage

Index tumor biopsy will be obtained day 8 (+/-5) of cycle 2. Blood will be drawn for PBMC and serum prior to treatment infusion on Day 1 of Cycle 1, 2, and 3, on Day 8 of Cycle 1, 2, and 3, and at the safety follow-up after treatment discontinuation.

Source and Timing of Biospecimen Collections

Standard biopsy is required to prove metastatic or recurrent disease and archival tissue will be obtained from that biopsy whenever possible.

Whole blood specimens (10 mL each for PBMC and Serum, in separate tubes) will be collected and sent on ice immediately to the UW H&N SPORE Pathology Core facility or the [name] lab for processing and storage.

Index tumor biopsies (research biopsy) will be performed by core needle, punch, or incisional technique at the discretion of the surgeon/interventional radiologist. Tissue from these biopsy specimens will be used, in order of availability, for formalin-fixed paraffin embedded histology and flash frozen in an Eppendorf tube. Surplus tissue should be flash frozen.

Banking of Leftover Biospecimens

Subject consent will be obtained to bank any leftover samples that were collected for study-specific correlative research. The UW H&N SPORE Pathology Core facility and/or the [name] lab will manage the banked samples.

Confidentiality of Biospecimens

Samples will be identified by a subject's study number assigned at the time of registration to the trial. Any material issued to collaborating researchers will be anonymized and only identified by the subject's study number and specimen description.

8. ASSESSMENT OF SAFETY

8.1. Specification of Safety Parameters

The Investigator should elicit information regarding the occurrence of AEs through open-ended questioning of the subject, physical examination, and review of laboratory results. AE data collection and reporting, which are required as part of every clinical trial, are done to ensure the safety of participants enrolled in the studies as well as those who will enroll in future studies using similar agents. AEs are reported in a routine manner at scheduled times during a trial. Additionally, certain AEs must be reported in an expedited manner to allow for optimal monitoring of participant safety and care. The first step is to identify the event using the NCI CTCAE version 5.0. The CTCAE document provides descriptive terminology for adverse event reporting. A grading (severity) scale is provided for each AE term.

All AEs, whether serious or not, will be described in the source documents and the AE page of the eCRF. All new events, as well as those that worsen in intensity or frequency relative to baseline, that occur after administration of study drug through the period of protocol-specified follow-up must be captured.

Specific anticipated AEs are described in section 2.3.

Information to be reported in the description of each AE includes but is not limited to:

- Medical diagnosis of the event. (If a medical diagnosis cannot be determined, a description of each sign or symptom characterizing the event should be recorded.)
- The date of onset of the event
- The date of resolution of the event
- Whether the event is serious or not
- Action taken

- Outcome
- Relatedness to the study drug and expectedness (see below)
- Subject's condition is intermittent or continuing
- The grade of the event based on the CTCAE v5.0

8.1.1. Unanticipated Problems (UPs)

The Office for Human Research Protections (OHRP) considers UPs involving risks to subjects or others to include, in general, any incident, experience, or outcome that meets **all** of the following criteria:

- unexpected in terms of nature, severity, or frequency given (a) the research procedures that are described in the protocol-related documents, such as the IRB-approved research protocol and informed consent document; and (b) the characteristics of the subject population being studied;
- related or possibly related to participation in the research (“possibly related” means there is a reasonable possibility that the incident, experience, or outcome may have been caused by the procedures involved in the research); and
- suggests that the research places subjects or others at a greater risk of harm (including physical, psychological, economic, or social harm) than was previously known or recognized.

8.1.2. Adverse Events (AEs)

An AE is any untoward medical occurrence whether or not considered related to the study drug that appears to change in intensity during the course of the study. The following are examples of AEs:

- Unintended or unfavorable sign or symptom
- A disease temporally associated with participation in the protocol
- An intercurrent illness or injury that impairs the well-being of the subject

Abnormal laboratory values or diagnostic test results constitute AEs only if they induce clinical signs or symptoms or require treatment or further diagnostic tests.

Hospitalization for elective surgery or routine clinical procedures that are not the result of an AE (e.g., surgical insertion of central line) should not be recorded as an AE.

Disease progression should not be recorded as an AE, unless it is attributable to the study regimen by the site investigator.

8.1.3. Serious Adverse Events (SAEs)

A serious adverse event is defined as any adverse event that meets one or more of the following criteria:

- Results in death; OR
- Is life-threatening; OR
- Requires hospitalization or prolongs existing hospitalization; OR
- Results in significant or persistent disability or incapacity; OR
- Results in a congenital anomaly/birth

Planned hospitalizations for disease-related surgery, routine procedures, non-disease-related procedures, and grade 3 toxicities listed in section 2.6.1.2 are not considered SAEs.

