2.3. Tertiary/Exploratory

Objective	Brief Description/Justification of Outcome Measure	Outcome Measured By	Time Frame
Evaluate each subject's tumor expression of PD-L1 by histology and determine whether this predicts response to NKTR-214, palliative RT, and anti-PD-1 therapy.	PD-L1 expression has been shown to predict response to immunotherapy regimens. If PD-L1 expression correlates with outcome, it could be used in the future to select patients who have greatest benefit from this regimen.	• Expression of PD-L1 by histology	• Baseline • Cycle 2, Day 8
Evaluate the immunologic activation induced by NKTR-214, palliative RT, and anti-PD-1 using serologic and flow cytometry immune assays and T cell receptor sequencing.	Evaluation of the in vivo immune response will help better define the mechanism of action of this combination therapy.	• Levels of IFN- γ expressing and CD122+ T cells in Peripheral Blood Mononuclear Cells (PBMC) • Diversity and clonality of the T cell receptor repertoire by deep sequencing of PBMC	• Cycle 1, 2, and 3, Day 1 prior to treatment infusion • Cycle 1, 2, and 3, Day 8 • 30 days post-treatment
Evaluate for histological evidence of antitumor activity based on the cellular phenotype of infiltrate.	Evaluation of the in vivo immune response will help better define the mechanism of action of this combination therapy.	• Levels of tumor infiltrating lymphocytes by histology	• Baseline • Cycle 2, Day 8

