3. STUDY DESIGN

This is a Phase II study to characterize the efficacy of NKTR-214 in combination with palliative radiation, and anti-PD1 in metastatic head and neck cancer patients. These patients very frequently require palliation of local symptoms with radiation in combination with systemic therapies and currently have very limited systemic options, making this an ideal population for investigation of NKTR-214 combination therapy. The study has been designed as a phase II due to the results of PIVOT-02, which demonstrate safety of anti-PD1 and NKTR-214 at the doses utilized in this study. The palliative radiation therapy delivered is unlikely to significantly increase toxicity. We will conduct efficacy evaluation on 24 participants. Under the null hypothesis for ORR ≤ 0.22 , based on one-sided one sample proportion test with type I error of 0.1, the expected power levels to detect alternative ORRs of 0.35, 0.4, and 0.45 are 55 %, 74 %, 87 % respectively. The null hypothesis will be rejected and superiority concluded if 8 or more responses are observed in 24 participants. This design yields a type I error rate of .04 and power of 0.8 when the true response rate is 44 %.

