8.4.2. Serious Adverse Event Reporting

Depending on the nature, severity, and attribution of the serious adverse event an SAE report will be phoned in, submitted in writing, or both according to Table 1 below. All SAEs must also be reported to the UWCCC DSMC. All SAEs must also be reported to the UW IRB (if applicable), and any sponsor/funding agency not already included in the list.

Determine the reporting timeline for the SAE in question by using the following table.

Table 1: FDA Reporting Requirements.

Phase 1 and Early Phase 2 Studies: Expedited Reporting Requirements for Adverse Events that Occur on Studies under an IND/IDE within 30 Days of the Last Administration of the Investigational Agent/Intervention 1,2 FDA Reporting Requirements for Serious Adverse Events (21 CFR Part 312)

NOTE: Investigators **MUST** immediately report to the UWCCC DSMC, Nektar Therapeutics, and the IRB (if applicable) and any other parties outlined in the protocol ANY SAE, whether or not they are considered related to the investigational agent(s)/intervention (21 CFR 312.64).

An adverse event is considered serious if it results in ANY of the following outcomes:

- 1) Death.
- 2) A life-threatening adverse event (the subject was at risk of death at the time of the event; it does not refer to an event that hypothetically might have caused death if it were more severe).
- 3) An adverse event that results in inpatient hospitalization or prolongation of existing hospitalization for \geq 24 hours. *
- 4) A persistent or significant incapacity or substantial disruption of the ability to conduct normal life functions.
- 5) A congenital anomaly/birth defect.
- 6) Important Medical Events (IME) that may not result in death, be life threatening, or require hospitalization may be considered serious when, based upon medical judgment, they may jeopardize the subject and may require medical or surgical intervention to prevent one of the outcomes listed in this definition (FDA, 21 CFR 312.32; ICH E2A and ICH E6).

ALL SAE that meet the above criteria **MUST** be immediately reported to the UWCCC DSMC and Nektar within the timeframes detailed in the table below:

Hospitalization	Grade 1 and Grade 2 Timeframes	Grade 3-5 Timeframes
Resulting in hospitalization \geq 24 hours	10 Calendar Days	
Not resulting in Hospitalization \geq 24 hours	Not required	24 Hour; 5 Calendar Days

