***Planned hospitalizations for disease-related surgery, routine procedures (such as G-tube placement), non-disease-related procedures, and grade 3 toxicities listed in section 2.6.1.2 will be exempt from SAE reporting as they are not dose limiting toxicities.**

Expedited AE reporting timelines are defined as:

- **24-Hour; 5 Calendar Days** – The AE must initially be reported within 24 hours of learning of the AE, followed by a complete expedited report within 5 calendar days of the initial 24-hour report.
- **10 Calendar Days** – A complete expedited report on the AE must be submitted within 10 calendar days of learning of the AE.

Serious adverse events that occur more than 90 days post completion of therapy, only SAEs with the attribution of possibly, probably or definitely will require reporting as follows:

Expedited 24-hour notification followed by complete report within 5 calendar days for:

- All Grade 3, 4, and 5 AEs

Expedited 10 calendar day reports for:

- Grade 2 AEs resulting in hospitalization or prolongation of hospitalization

Serious Adverse Event – Reported Within 24 Hours

Serious Adverse Events requiring reporting within 24 hours (as described in the protocol) must also be reported to the Data and Safety Monitoring Committee (DSMC) Chair via an email to [contact] within one business day. The OnCore SAE Details Report must be submitted along with other report materials as appropriate (NCI AdEERS form or FDA Medwatch Form #3500 and/or any other documentation available at that time of initial reporting). The DSMC Chair will review the information and determine if immediate action is required. Within 10 working days, all available subsequent SAE documentation must be submitted electronically along with a 24 hour follow-up SAE Details Report and a completed UWCCC SAE Routing Form to [contact]. All information is entered and tracked in the UWCCC database.

The Principal Investigator notifies all investigators involved with the study at the UWCCC, the IRB, the sponsor, and the funding agency and provides documentation of these notifications to the DSMC.

If the SAE occurs on a clinical trial in which the UW PI serves as the sponsor-investigator, the PI reviews the event to determine whether the SAE requires reporting to the FDA and other participating investigators.

For a multiple-institutional clinical trial the PI is responsible for ensuring SAEs are reported to the FDA as well as to all participating investigators.

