In the event the UWCCC Principal Investigator is acting as the Sponsor-Investigator (i.e., the PI holds the IND), the PI assumes responsibilities of the study sponsor in accordance with FDA 21 CFR 312.32. In this capacity, the UWCCC PI reviews all reports of serious adverse events occurring on the study at the UWCCC and participating external sites and makes a determination of 1) **suspectedness** (i.e., whether there is a reasonable possibility that the drug caused the AE); and 2) **unexpectedness** (the event is not listed in the Investigator's Brochure or is not listed at the specificity or severity that has been observed) in the context of this study. SAE with suspected causality to study drug and deemed unexpected are reported as IND Safety Reports by the UWCCC PI to the FDA, all participating investigators on the study, and the external global sponsor (if applicable) within 15 calendar days. All fatal or life-threatening SAE that are unexpected and have suspected causality to the study drug will be reported by the UWCCC PI to the FDA, all participating investigators on the study, and the external global sponsor (if applicable) within 7 calendar days.

Report to the UWCCC and Nektar

Reference the **SAE SOP** (Standard Operating Procedure) and the **SAE Reporting Workflow for DOTs** on the UWCCC website (<http://kb.wisc.edu/uwccc>) for specific instructions on how and what to report to the UWCCC for [24] hour initial and follow-up reports. **A follow-up report is required to be submitted within 10 days of the initial [24] hour report.**

For this protocol, the following entities are required to be notified:

- a. [contact]
- b. Study Chairs: [name], PhD and [name]
- c. UWCCC PIs: [name] [name] and [name], PhD
- d. UWCCC PM: [name]
- e. Nektar Therapeutics ([contact])
- f. Any other appropriate parties listed on the SAE Routing Form (for follow-up reports only)

Report to the IRB

Consult the UW-IRB website for reporting guidelines.

Reported within 10 Calendar Days

SAE requiring reporting within 10 calendar days (as described above) must also be reported to the DSMC Chair via an email to [contact]. SAEs will also be reported to Nektar in the same timeframe. The SAE Details Report must be submitted along with other report materials as appropriate. The UWCCC DSMC Chair will review the information and determine if further action is required. All information is entered and tracked in the UWCCC database.

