14.5. Subject Confidentiality

Subject confidentiality is strictly held in trust by the investigators, study staff, and the study sponsor(s) and their agents. This confidentiality is extended to cover testing of biological samples and genetic tests in addition to any study information relating to participants.

The study protocol, documentation, data, and all other information generated will be held in strict confidence. No information concerning the study or the data will be released to any unauthorized third party without prior written approval of the study sponsor.

The study shall be conducted in full compliance with (i) all applicable laws, regulations, and guidance of Regulatory Authorities relating to human clinical research of the type described in the Protocol, including the United States Federal Food, Drug and Cosmetic Act ("FDC Act") and the relevant provisions of Title 21 of the United States Code of Federal Regulations; (ii) generally accepted standards of Good Clinical Practice ("GCP"), including ICH E6 Good Clinical Practice: Consolidated Guidance (April 1996) as adopted by the FDA; and (iii) all applicable laws relating to the collection, use, storage and disclosure of individually-identifiable patient medical information, records and data, including but not limited to the Health Insurance Portability and Accountability Act of 1996 as amended by the Health Information Technology for Economic and Clinical Health Act of 2009 and similar state, local and foreign laws (collectively "Privacy and Security Regulations").

Regulatory Authorities will have access to any and all of the following as may be required by applicable law and regulations or guidances of Regulatory Authorities: (i) the Principal Investigator, any other Investigator, or other personnel involved with the Study; (ii) Study facilities; and (iii) books, accounts, Study Drug records, patient records, case report forms, source data (as that term is defined and used in ICH E6 Good Clinical Practice: Consolidated Guidance (April 1996)), and other records, documents, materials and sources of information related to the Study ("Records").

AEs will be reported to Regulatory Authorities promptly in compliance with applicable law. In addition, any Serious Adverse Event ("SAE") will be reported to Nektar within 24 hours from the time it is determined by study personnel that such an event or reaction has occurred, or immediately if the event or reaction is fatal or life-threatening.

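### The SAE exemption for grade 3 toxicities points to a section that does not exist, and 8.4.2 and 14.5 set different supplier deadlines for grade 1-2 SAEs

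*Combined protocol and SAP*

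**What the plan says.** **The exemption.** Section 8.1.3 gives five criteria for a serious adverse event and then adds that certain planned hospitalisations and "grade 3 toxicities listed in section 2.6.1.2 are not considered SAEs". A starred note in 8.4.2 repeats this with a reason: "grade 3 toxicities listed in section 2.6.1.2 will be exempt from SAE reporting as they are not dose limiting toxicities".

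**The general reporting rule.** Section 8.4.2 tells investigators to report immediately to the DSMC, the supplier and, if applicable, the IRB "ANY SAE, whether or not they are considered related to the investigational agent(s)/intervention".

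**The supplier deadline.** Section 14.5 says that any SAE "will be reported to Nektar within 24 hours" of study personnel determining that it has occurred, and immediately if it is fatal or life-threatening. Table 1 in 8.4.2 applies its own timeframes to the DSMC and the supplier, by grade and by whether hospitalisation lasted at least 24 hours. The later text of 8.4.2 on the 10-calendar-day class states: "SAEs will also be reported to Nektar in the same timeframe".

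**Collection windows.** Section 8.2 collects AEs starting up to 30 days after the end of treatment. It collects SAEs starting up to 90 days after, or until a new anti-cancer therapy begins. Beyond 90 days it records only SAEs that are at least possibly related.

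**The concern.** An exemption from the SAE definition is an operative rule: site staff apply it event by event. With the list missing, two people can classify the same hospitalised grade 3 event differently and both claim to follow the protocol. The classification decides whether the event gets expedited notice to the DSMC and supplier and the sponsor-investigator's causality and expectedness review. After day 30 it may also decide whether the event is collected at all.

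This matters more here than in many phase II trials. Section 1.1.3 says that dose escalation of the triple combination was forgone, and 4.6 gives no numerical safety stopping rule. Much of the oversight therefore rests on the flow of SAE reports and the quarterly summaries to the DSMC (9.1 and 9.1.1).

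The two supplier deadlines are a separate inconsistency, but the same kind of problem: one event with two instructions.

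**Working it through.** No sample size, error rate or event count enters this point. The check sets the sections side by side.

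**1. Does section 2.6.1.2 exist?** Section 2 contains 2.1, 2.2 and "2.3. Tertiary/Exploratory". The next heading is "3. STUDY DESIGN". There is no 2.4, 2.5 or 2.6. The pages removed from the public file come before the body of Section 2, so removal does not explain the gap.

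**2. Can the target be recovered by renumbering?** Two other stale references look shifted by one section. Section 8.1 cites 2.3 for anticipated AEs, but the risks are in 1.3. Section 7.1.5 cites Section 9 for AE assessment, but that is Section 8. The same shift would give 1.6.1.2, and Section 1 ends at 1.3. Renumbering does not identify the list.

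**3. What is the likeliest target?** The only itemised list of grade 3 toxicities is in 8.3.2 (items a to j, plus grade 3 radiation mucositis and dermatitis in the text above it). The safety objective in 2.2 cites 8.3.2 by its correct number; neither exemption does. Treating 8.3.2 as the target is therefore an assumption.

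**4. Does the stated reason help?** Not being dose limiting is not among the five seriousness criteria in 8.1.3 or the six in Table 1. The protocol mentions dose limiting toxicity only for an earlier trial (1.1.3) and defines none for this one.

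**5. What would change if 8.3.2 is meant?** Take a grade 3 infection that leads to hospitalisation and resolves in under a week (item j).

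- *On treatment or up to day 30 after it:* it meets the hospitalisation criterion, but the exemption removes SAE status. It is still recorded, because 8.1 requires all AEs, serious or not, on the case report form.
- *Starting on days 31 to 90:* the AE window has closed at day 30. The SAE window is open to day 90, but the event is not an SAE. It falls outside both windows for up to 90 − 30 = 60 days, or less if new anti-cancer therapy starts. Long-term follow-up in 6.6 documents only related AEs above grade 3, so it does not recover this event.

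Items a, b, g and h are tied to an infusion or cycle and would rarely arise that late. Items c, d, e, f, i and j carry no such tie.

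**6. Supplier deadline by class of SAE.**

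| SAE | 14.5 | 8.4.2 |
|---|---|---|
| Grade 1-2, hospitalised at least 24 hours | 24 hours | 10 calendar days = 10 × 24 = 240 hours |
| Grade 1-2, not so hospitalised | 24 hours | no report required |
| Grade 3-5 | 24 hours, or immediately if fatal or life-threatening | 24-hour initial report, complete report within a further 5 calendar days |

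For the first class the limits differ by 240 / 24 = 10 times. For the second, one section requires a report and the other does not. The grade 3-5 row assumes that the one empty cell in the extracted table was merged with its neighbour. The rule in 8.4.2 for events after 90 days, which puts all grade 3-5 events on a 24-hour notice, supports that reading.

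**The case against.** Several stronger readings are tempting, and the documents do not support them.

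**That hospitalised toxicities would vanish from DSMC review.** They would not. Section 8.1 records all AEs, the quarterly summaries in 9.1.1 cover toxicities as well as SAEs, and 9.1 has significant toxicities discussed at regular team meetings. The grade 3 or higher treatment-related rate in 11.3.2 does not depend on SAE status. At risk are the SAE label, the expedited route and some late events.

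**That the exemption flatly contradicts the rule on any SAE.** The wording "ANY SAE, whether or not they are considered related to the investigational agent(s)/intervention" removes a causality filter. An event outside the SAE definition is not caught by a rule about SAEs. In Table 1 the exemption also hangs on the hospitalisation criterion alone, so fatal, life-threatening or disabling events stay reportable there. What remains is a difference of scope: 8.1.3 does not limit the exemption to hospitalisation. It also lacks Table 1's important-medical-event criterion and 24-hour threshold.

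**That ten whole categories move in or out of the SAE count.** This needs 8.3.2 to be the intended list. Even then, only events that also meet a seriousness criterion would move, and most items are limited by duration or resolution.

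**That the deadline differs tenfold for SAEs in general.** It does so only for grade 1-2 SAEs with hospitalisation of at least 24 hours.

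Three further points weigh on the other side. The exemption can be read as covering only planned admissions for these toxicities, although the reason in 8.4.2 speaks of the toxicities themselves. Section 8.1 also asks for capture of new events through protocol-specified follow-up, which could be read as extending past the 30-day limit in 8.2; the two are not reconciled. And a site that meets 24 hours also meets 10 days, so staff can satisfy both deadlines. None of this defines the exempt set or says which deadline governs.

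**Conclusion.** Two defects stand. First, the exemption in 8.1.3 and 8.4.2 has no determinable content, and its stated reason does not bear on seriousness. If 8.3.2 is the intended list, hospitalised grade 3 events on it lose SAE status, expedited DSMC and supplier notice, and sponsor SAE review, and those starting 31 to 90 days after treatment could go uncollected. That consequence is conditional, and the documents give no basis for estimating how many events it would involve. Second, for grade 1-2 SAEs the supplier deadline is 24 hours in 14.5, against 10 calendar days or no report in 8.4.2. Grade 3-5 events appear consistent, on the merged-cell reading of Table 1.

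The primary ORR analysis is unaffected. These are internal inconsistencies in safety-reporting rules that cannot be applied uniformly as written. They should be corrected because the rules are operative and the correction is cheap.

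**What to change.** Reconcile 8.1.3 with both statements in 8.4.2:

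- Delete the toxicity exemption, or point it to a list that exists in the protocol. Remove the reference to dose limiting toxicity.
- State that events meeting a seriousness criterion, including unplanned hospitalisation, are still recorded and shown to the DSMC. If an exemption is kept, say that this also holds from day 31 to day 90 after treatment.
- Use one set of seriousness criteria in 8.1.3 and Table 1.
- State one supplier timeline in 8.4.2 and 14.5, covering grade 1-2 SAEs with and without hospitalisation of at least 24 hours.

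The sponsor should choose which rule applies in each case; the documents do not settle it. The cost is protocol wording, and a few more SAE forms if the exemption is removed.
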